Feasibility and Acceptability of Mobile Mantram
Repetition Program for Veterans With PTSD
(IVI 22-115)

NCT05998967

August 12, 2021

SPECIFIC AIMS

Easily accessible interventions to address post-traumatic stress disorder (PTSD) can play critical role in reducing PTSD and associated symptoms in Veterans, especially for those who remain symptomatic after treatment with other evidence-based interventions, those who prefer complimentary and integrative therapies, or those who have difficulty accessing traditional face-to-face mental health services. The value of these programs is their ability to provide Veterans with more options in their recovery journey and to reach a broad range of Veterans across multiple settings, including remote rural contexts.

The Mantram Repetition Program (MRP) is a meditation-based practice that consists of the repetition of a spiritual word, one-pointed attention, and slowing down. MRP has been shown to reduce stress in several high-risk populations, and two large randomized, controlled studies show that MRP reduces PTSD symptoms among Veterans. A brief, web-based, self-directed version of MRP has been developed to increase the accessibility of evidence-based PTSD treatment. This version of MRP was tested in a pilot study with undergraduate students, demonstrating its ease of use and success in getting students to engage with the practice. The proposed mixed method study will use the Reach, Effectiveness, Adoption, Implementation, Maintenance (RE-AIM) framework to evaluate the mobile MRP in Veterans with PTSD in two conditions: self-directed and with text/phone support. Data from this pilot study will inform the refinement of the MRP delivery strategy and the development of a full-scale trial to test its effectiveness and implementation outcomes, as well as barriers and facilitators, and other contextual factors.

Aim 1. To assess the reach and implementation of the mobile Mantram Repetition Program using a mixed methods approach focusing on feasibility, acceptability, appropriateness, and facilitators of and barriers to program implementation.

Aim 2. To compare Veterans who are self-directed users of mobile MRP versus Veterans who receive text and phone support in terms of engagement with the intervention and change in PTSD and associated symptoms.

BACKGROUND AND SIGNIFICANCE

Posttraumatic stress disorder (PTSD) is common among US military Veterans (Gradus, 2007). Untreated, PTSD is chronic and highly impairing (Santiago et al., 2013) thus it is a high priority for the VA. Current evidence-based treatments can be highly effective; nonetheless, many Veterans remain symptomatic even after successful treatment (Steenkamp et al., 2020). Further, many Veterans express a preference for alternative approaches or complements to other treatment strategies (Whitehead & Kligler, 2020). Consistent with the Hannon Act, both meditation and spiritually-based approaches are potentially important avenues for restoring Whole Health for Veterans.

The Mantram Repetition Program (MRP) is a meditation-based approach that involves silent repetition of a spiritual word in combination with development of one-pointed attention and slowing down (Bormann et al., 2014). The MRP is a transdiagnostic intervention, with documented positive effects on a range of outcomes, including improved stress management among healthcare workers (e.g., Leary et al, 2018) and caregivers (e.g., Bormann et al., 2009) and better coping among individuals with HIV (e.g., Bormann et al., 2006). Importantly, **two large randomized controlled trials with Veterans have demonstrated that MRP was associated with large effect size reduction symptoms of PTSD** as well as increased spiritual well-being and reduced insomnia (Bormann et al., 2012, 2018). The MRP can be taught in person or remotely, including by use of pre-recorded videos or by clinicians, paraprofessional or lay people. For example, the MRP was recently applied to increase patient-centered care and decrease burnout in nurses via internet-based learning (Kostovich et al., 2021). Recent work in our lab demonstrated that MRP can be taught in a self-directed manner through a series of brief videos delivered via Qualtrics. This brief, self-guided, web-based version of MRP was implemented with an undergraduate student sample and showed good retention in the program (88% completed the full intervention and 87% completed the follow-up assessment). Mantram repetition was regularly utilized by 80% of the group, and 96% endorsed applying the concept of slowing down. On average, participants were practicing 4-5 days/week (Vannini, et al, 2021). These initial data on the feasibility and acceptability of this MRP implementation strategy show promise for use in Veterans, given the demand for a wide range of easily-accessible and complementary and integrative treatment options.

eScreening is a web-based, patient-facing screening and information-provision system developed with Veteran and staff feedback that allows for the rapid capture of self-report data and has been shown to improve the quality of documentation and access to care (Pittman et al., 2019). Across multiple VHA facilities, eScreening has been utilized over 34,000 times with Veterans in Transition Care Management, primary care, and mental health settings; eScreening supports both screening and measurement-based deployment of evidence-based psychotherapy. In 2016, the eScreening program was named a Gold Standard Practice for diffusion throughout VHA by the Under-Secretary for Health (Elnahal et al., 2017). eScreening is available nationwide and is a promising platform for the delivery of MRP to Veterans.

The goals of this study are to (1) better understand mobile MRP by measuring reach, feasibility, acceptability, appropriateness, barriers and facilitators; and (2) compare effectiveness (i.e., mantram use, PTSD and associated symptoms) of self-directed MRP (i.e., used without support from a facilitator) to supported MRP (i.e., text/phone support provided by a facilitator) in Veterans with PTSD using the existing VA eScreening platform for delivery of the program.

This project is responsive to several HSR&D priorities. If successful, this program would enhance access to care, thereby increasing health equity through the utilization of virtual care. This project also targets PTSD and associated symptoms, including insomnia, important mental health issues prioritized by HSR&D. This project features meditation, which is of interest to an increasing number of Veterans and a potential component of the Whole Health approach, whereby Veterans may focus on overall wellness, including spirituality. Finally, this study uses eScreening, an electronic, self-report screening system, developed by our research group for data collection and access to the intervention videos. Consistent with the aims of the SWIFT-IVI program, we will pilot an implementation strategy in preparation for a future fully-powered implementation trial with the aim of rapidly deploying the MRP into routine practice.

METHODS

Study Design

This study is a prospective, randomized trial assessing implementation and effectiveness outcomes of a brief, self-directed, web-based meditation training. We will employ a mixed-method convergent approach to collect and analyze data to inform future implementation of the MRP (Palinkas et al., 2019).

Participants

Participants will be 40 Veterans with PTSD residing in San Diego County, CA. These individuals will be recruited from VA clinics (self- and provider-referral) and through community outreach (e.g., advertisements). Eligibility is intentionally broad to approximate future real-world users of MRP.

Inclusion: Veteran, 18 or older, primary clinical complaint of PTSD, ability to access internet-enabled smart phone, tablet, or computer.

Exclusion: Cognitive impairment or mental health concerns that necessitate a higher level of care or interfere with the ability to consent or engage in study activities (serious mental illness, untreated alcohol or substance use disorder, serious suicidality or homicidality, marked cognitive impairment).

Interventions

MRP consists of four online training modules that were developed for a Veteran audience by [name], the developer of the intervention. They cover the basic intervention components: choosing a mantram, slowing down, attentional control and habit formation. These videos were created in conjunction with PsychArmor, Inc., a non-profit organization that provides training to multiple sectors who support Veterans and are available via internet (refer to Letter of Support from [name]). In the **self-directed condition**, enrolled Veterans will not be contacted unless they reach out using contact information in the weekly module. In the **supported condition**, Veterans will receive a daily text reminder to practice their mantram (e.g., "Did you find a moment to practice your mantram today? Please respond YES, NO or HELP if you would like to talk to one of our staff."). Those who answer in the affirmative will receive praise and an offer of support (e.g., "Great job! A regular practice happens one day at a time!"). Those who answer in the negative will receive brief encouragement and an offer of assistance (e.g., "You can repeat your mantram at any spare moment. Would you like to speak with a trainer about working it into your day?"). A request for help will be followed by a personal text and call by study staff.

Procedures

Following provision of written informed consent and HIPAA authorization using a telehealth-based informed consent process, Veterans will confirm access to a study-compatible device (Internet-enabled smart phone, tablet or computer) and be administered a semi-structured interview (MINI) and brief cognitive screen (blind MoCA) via telephone by a trained Research Assistant (RA) to confirm eligibility. If deemed eligible, the Veteran will be randomly assigned to one of two conditions: self-directed MRP or supported MRP. Veteran involvement then proceeds as follows:

1. Veterans complete a brief assessment battery (see **Measures**) including demographics and mental health symptoms using eScreening.
2. Veterans access the training videos via eScreening.
 - a. Day 1: All complete a brief symptom screener (see **Measures**), watch a ~15-minute instructional video (#1) and answer comprehension and credibility questions about the video.
 - b. Days 2-7: *Supported condition only*: They are prompted daily to engage in meditation practice and may receive support toward that end (see **Interventions**).
 - c. Day 8: All complete a brief symptom screener and questions about meditation practice, watch a ~15-minute instructional video (#2), and answer comprehension questions about the video.
 - d. Days 9-14: *Supported condition only*: Daily prompts/support.
 - e. Day 15: All complete a brief symptom screener and questions about meditation practice, watch a ~15-minute instructional video (#3), and answer comprehension questions about the video.
 - f. Days 16-21: *Supported condition only*: Daily prompts/support.
 - g. Day 22: All complete a brief symptom screener and questions about meditation practice, watch a ~15-minute instructional video (#4), and answer comprehension questions about the video.
 - h. Days 23-28: *Supported condition only*: Daily prompts/support.

- Veterans complete a brief assessment battery about mental health symptoms and answer questions about the feasibility, acceptability, and appropriateness of mobile MRP (Weiner et al., 2017).

Data Collection and Measures

We will collect data for the reach, implementation, and effectiveness outcomes of RE-AIM (Glasgow et al., 2019) as depicted in Table 1. In this study, we will not be focusing on the last two dimensions of RE-AIM (i.e., adoption and maintenance). The advantage of this mechanism for delivering MRP is that it is self-directed, requiring little or no support from providers, and utilized similarly to other VA apps (e.g., PTSD Coach); consequently, factors related to the providers' adoption of mobile MRP are minimal. Collection of data pertaining to maintenance is beyond the scope of this one-year study, but it will be an important factor to measure in the full-scale trial of this self-directed adaptation of the delivery of MRP with or without support in Veterans with PTSD.

RE-AIM	Definition	Measure/Instrument	Data source
Reach	The absolute number, proportion, and representativeness of participants	Number of screenings Percent eligible/ineligible Refusal rate Characteristics of participants	Study recruitment logs eScreening platform surveys
Implementation	How much and how well the MRP is implemented and how it is received by Veterans	Acceptability of Intervention Measure (AIM) Intervention Appropriateness Measure (IAM) Feasibility of Intervention Measure (FIM) Credibility of MRP % of videos completed with comprehension Satisfaction with MRP Mantram use	eScreening platform surveys Qualitative interview
Effectiveness	The impact of an intervention on Veteran outcomes	Brief Symptom Screen PCL-5 PHQ-9 ISI Brief PHI	eScreening platform surveys

Screening

The Mini International Neuropsychiatric Interview (**MINI 7.0**) (Sheehan et al., 1998) will be used to assess suicidality, substance dependence, and serious mental illness. **Blind MoCA** (Wittich, et al., 2010), which is a version of the Montreal Cognitive Assessment that can be used to assess for cognitive impairment via videoconferencing, will assess cognitive readiness to participate. **Demographic characteristics** include age, gender, race/ethnicity, relationship status, years of education, SES/income/living situation, residential ZIP code, occupation/work status, branch of service/highest rank, service connection/disability status.

Reach Measures

The **number of screenings**, **percent eligible/ineligible**, and **refusal rate** will be calculated, and **characteristics** of participating Veterans with PTSD will be compared those who refuse or are ineligible and to clinical eScreening data from the facility to assess generalizability.

Implementation Measures

The Acceptability of Intervention Measure (**AIM**), Intervention Appropriateness Measure (**IAM**), and Feasibility of Intervention Measure (**FIM**) developed by Weiner et al, 2017) will be used to calculate mean ratings of acceptability, appropriateness, and feasibility. A **Qualitative Interview** will be used to collect additional qualitative data on the AIM, IAM, FIM using the interview guides that we have previously modified for use in our other studies (McCreight et al., 2019; Pittman et al., 2021). We will also explore barriers and facilitators of the implementation of MRP. **Credibility ratings** of the intervention will be assessed with three items adapted from Borkovec & Nau (1972). Ratings that are comparable to previous studies using mantram suggest that acceptability is retained in this format. **Comprehension Questions** will be module-specific and test the participants' knowledge and understanding of each video. Using a conservative approach, we will not consider a video completed unless the comprehension question is answered successfully. The questions were developed for the Vannini et al. (2021) pilot of mobile MRP. **Satisfaction** will be assessed using a set of five-point Likert scale (1 =very dissatisfied; 5=very satisfied) items rating the module narrator, learning outcomes, overall course, and module content. The **Mantram Use Scale**, which has been used in several MRP efficacy studies, queries aspects of mantram use (frequency, practice/coping, sleep).

Effectiveness Measures

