Quantitative Analysis. Quantitative data from surveys and study databases will be summarized using descriptive statistics including frequencies, proportions, measures of central tendency (mean and median), and variability (standard deviation and interquartile range) along with data visualization methods, such as frequency tables, bar charts, line graphs, and scatter plots to understand implementation and effectiveness outcomes. 95% confidence intervals will be calculated when estimating proportions and means. Change from baseline to each post-intervention on effectiveness measures and mantram use will be calculated overall and by group (self-directed vs supported). Wilcoxon signed rank test and rank sum test will be used to examine the change in each group and compare the change between two groups. Linear mixed effects model will be used to examine the trajectory of change from baseline to post-intervention.

Qualitative analysis. Interviews will be recorded and transcribed. All qualitative data will be coded using a rapid qualitative data analytic approach. Unique and common themes across the two groups will be compared. Data analysis will be led by Drs. [name] and [name] and will also include qualitatively-trained members of the research team.

A matrix approach will be used to triangulate data from quantitative and qualitative sources. We will use a joint display analysis to support the integration of different data sources and types. Unique and common themes emerging across the two groups (self-directed and supported) will be identified and described.

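### The acceptability, appropriateness and feasibility scales are given once, after the four-week program, so Veterans who stop early are likely to be under-represented in the mean

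*Combined protocol and SAP*

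**What the plan says.** Specific Aims sets Aim 1 as an assessment of reach and implementation "focusing on feasibility, acceptability, appropriateness, and facilitators of and barriers to program implementation". Three short scales measure these directly: the AIM, IAM and FIM.

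Procedures lists the study contacts in order. The last lettered step is "Days 23-28: *Supported condition only*: Daily prompts/support". After it comes a closing battery in which Veterans "answer questions about the feasibility, acceptability, and appropriateness of mobile MRP". The three scales are scheduled nowhere else. The closing step has no day number of its own, so its timing is read from its position in the list.

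Implementation Measures says that the scales "will be used to calculate mean ratings of acceptability, appropriateness, and feasibility". Under Data Analysis, "95% confidence intervals will be calculated when estimating proportions and means". Neither section says whose ratings enter the mean or what happens when a rating is missing.

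Two other provisions bear on the point. Table 1 gives eScreening surveys and the qualitative interview as the data sources for implementation outcomes, and Procedures uses eScreening to deliver the videos. Under Interventions, staff do not approach a self-directed Veteran who has not made contact first, whereas supported Veterans get a daily text.

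**The concern.** For most outcomes, stopping early and the outcome are separate things that may be correlated. For acceptability the link is closer, because finding a program unacceptable is one plausible reason to stop using it. With a single late rating on the same platform as the program, a Veteran who stops opening eScreening in week one or two may leave no AIM, IAM or FIM score. The reported mean would then lean towards those who stayed.

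These ratings are meant to inform refinement of the delivery strategy and the design of a full-scale trial. An inflated mean could make the program look better received than it was. If disengagement is more common without support, the self-directed mean would be inflated more, which would shrink any apparent advantage of support. A rating that was never collected cannot be recovered at analysis.

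**Working it through.** The documents state no figure for this bias, so there is none to reproduce. The check has two parts.

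**1. Schedule.** Content of each contact in Procedures:

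- Pre-program battery: demographics and mental health symptoms.
- Day 1: symptom screener, video #1; Veterans "answer comprehension and credibility questions about the video".
- Days 8, 15 and 22: symptom screener, practice questions, videos #2 to #4, comprehension questions.
- Days between: prompts and support, supported arm only.
- Closing step: symptom battery plus AIM, IAM and FIM.

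So the three scales are given once. The linear mixed model under Data Analysis concerns change from baseline and cannot supply a rating that was only ever taken at the end.

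**2. Size, under assumptions.** Let *r* be the proportion who rate, *M_R* the mean of raters and *M_N* the mean that non-raters would have given. The mean over all randomised Veterans is *r·M_R + (1 − r)·M_N*, so

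bias = *M_R* − [*r·M_R + (1 − r)·M_N*] = (1 − *r*)(*M_R − M_N*).

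Inputs:

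- N = 40, 20 per group (Participants; Sample size).
- The only retention figures in the documents are from the undergraduate pilot (Background and Significance): "88% completed the full intervention and 87% completed the follow-up assessment". At 87%, 0.87 × 40 = 34.8, so about 35 rate and 5 do not.
- 8, 12 or 16 non-raters (20%, 30%, 40%) are assumed, because no dropout rate is stated for this trial.
- *M_R* = 4.2 and *M_N* = 3.5 or 2.5 are assumed, giving gaps of 0.7 and 1.7. The 1-5 range is also assumed; the documents do not give the range of these scales.

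| Non-raters of 40 | All-randomised mean, gap 0.7 | Bias | All-randomised mean, gap 1.7 | Bias |
|---|---|---|---|---|
| 5 | (35×4.2 + 5×3.5)/40 = 4.11 | 0.09 | (35×4.2 + 5×2.5)/40 = 3.99 | 0.21 |
| 8 | 4.06 | 0.14 | 3.86 | 0.34 |
| 12 | 3.99 | 0.21 | 3.69 | 0.51 |
| 16 | 3.92 | 0.28 | 3.52 | 0.68 |

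The range is about 0.1 to 0.7 points.

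**By arm.** Suppose 90% rate in the supported arm and 70% in the self-directed arm (assumed). The bias is 0.10 × 0.7 = 0.07 to 0.10 × 1.7 = 0.17 in the supported arm, and 0.30 × 0.7 = 0.21 to 0.30 × 1.7 = 0.51 in the self-directed arm. The self-directed mean is then inflated by 0.14 to 0.34 more. With equal response and equal gaps, the difference is zero.

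**Confidence interval.** With 35 raters the 95% half-width of a mean is about 0.34 SD. It describes sampling error among raters and does not cover this bias.

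**The case against.** The case on the other side is substantial, and several parts of it stand.

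- A reader might infer that early stoppers can never reach the scales. The documents do not say so. The closing step stands apart from the video steps and is not restricted to completers, so a Veteran can skip videos and still rate. Under-representation is likely, not certain.
- A reader might infer that Day 1 credibility is the only opinion an early stopper gives. That is not shown either: Satisfaction items are planned and their timing is not stated.
- A reader might infer that poor retention would be hidden. It would not. The share of videos completed, counted only with a correct comprehension answer, is an implementation measure, and precision is planned for feasibility rates such as initiation. Aim 1 is mixed-methods, and interview and survey data are set side by side.
- The sentence "Ratings that are comparable to previous studies using mantram suggest that acceptability is retained in this format" concerns the credibility items, which are taken on Day 1, before most stopping can occur. It is not evidence of the problem.
- A reader might take it as fact that the missing ratings are the low ones. Veterans may also stop for reasons of time, symptoms or access. At the pilot's retention with the smaller gap, the shift is only 4.20 to 4.11, and no decision threshold for these scales is stated.
- A Day 8 rating misses a Veteran who stops silently after video #1, and a carried-forward Day 8 rating reflects only part of the program. It should therefore not become the headline figure.

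These points limit the claim but do not remove it. Completion rates show that people left, not how they would have rated the program. The interview has no stated timing and no plan to include those who stopped. None of these measures puts an early stopper's rating into the AIM, IAM or FIM mean.

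**Conclusion.** The concern holds in a limited form. Core Aim 1 ratings are collected once, at the end, on the platform that a disengaging Veteran stops opening, and no written plan seeks ratings from those who stop. Early stoppers are therefore likely to be under-represented. Whether this biases the mean upwards depends on their ratings being lower, which is plausible but not stated. At 13% to 40% non-response and gaps of 0.7 to 1.7 points, the bias is about 0.1 to 0.7 points on an assumed 1-5 scale. Apart from the pilot's 87%, these inputs are assumptions.

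The documents do not support a claim that the mean is certainly inflated, that it represents completers only, or that Aim 1 cannot be answered. This is a worthwhile, low-cost improvement to data collection and reporting in a feasibility pilot.

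**What to change.** **Procedures.**

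- Add the AIM, IAM and FIM to the Day 8 eScreening session and keep them in the closing battery.
- State that every randomised Veteran is invited to the closing ratings whatever their program use. Make clear that this assessment invitation applies in the self-directed arm too, since the no-contact wording under Interventions leaves that open.
- Offer the same ratings at any known withdrawal.

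**Implementation Measures.**

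- Keep the end-of-study mean as the main figure.
- Report the number rating out of the number randomised, by arm.
- Add the mean of the last available rating as a sensitivity analysis.
- Reserve some of the planned qualitative interviews for Veterans who stopped before video #4.

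**Cost.** The change adds a few minutes of self-report in a session already scheduled, plus the wording changes. The sensitivity analysis pools ratings from different time points and should be labelled so. Veterans who stop silently after video #1 can be reached only through the closing invitation or the interviews, so the gap narrows but does not close.
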